4.2.5. Stopping Rules for Dose-limiting Toxicity

If 3 or more of the first 6 subjects or 4 or more of the first 10 or 40% of subjects or more in this cohort of 20 patients experiences a DLT during Cycle 1, accrual will stop pending consultations between the sponsor, BMS and the FDA.

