The study will consist of 4 periods: Screening (up to 4 weeks), Induction Treatment (up to 1 12-week cycle of induction therapy with ipilimumab and NIVOLUMAB), Treatment/Follow-up (up to 48 weeks of NIVOLUMAB), and Survival Follow-up. Each induction treatment cycle is comprised of 4 doses of NIVOLUMAB and 4 doses of ipilimumab given every three weeks for a total of 12 weeks (cycle 1) with a tumor assessment at the end of cycle 1 at week 12.

At the end of the Induction Treatment Period (Week 12) subjects without evidence of relapse radiologically and clinically will be able to continue to receive NIVOLUMAB treatment 480mg every 4 weeks for 48 weeks. Subjects who relapse at the disease evaluations at Weeks 12, 24 or later will not receive further treatment with NIVOLUMAB.

Patients who experience a DLT to NIVOLUMAB and ipilimumab during or after cycle 1 will not receive further treatment with NIVOLUMAB and ipilimumab.

Subjects who prematurely discontinue 1 or both study drugs will complete the remaining study visits and associated evaluations (without dosing of 1 or both study drugs, as applicable) indefinitely until withdrawal of consent for follow-up or death.

Dosing during cycle 1 will consist of: 3 mg/kg of NIVOLUMAB + ipilimumab at 1 mg/kg

Dosing during cycles 2-5 will consist of flat dose NIVOLUMAB at 480 mg

Since the drugs will be given concurrently, it will not be possible to attribute dose-limiting toxicities to one or the other drug during the first 12 weeks of therapy.

Subjects who withdraw from the study during Cycle 1 for reasons other than a DLT will be replaced.

No dose escalations or de-escalations are permitted within each subject's treatment. NIVOLUMAB or ipilimumab dose adjustments are allowed only if there has been $\pm 10\%$ weight change since the previous treatment (Induction/Treatment Period only). No dose escalations or de-escalations are allowed during cycles 2-5 due to the use of flat dosing of NIVOLUMAB at 480 mg every 4 weeks.

NUMBER OF SUBJECTS (PLANNED)

Up to 25 subjects (20 in this trial with five to account for drop-outs) will be enrolled in the study.

BLINDING AND RANDOMIZATION

This is an open-label study. Eligible subjects will be treated in the order they enter the study.

DIAGNOSIS AND MAIN CRITERIA FOR INCLUSION

Subjects will have no HLA restriction, and have a histological diagnosis of Stages IIIB/IIIC/IV Melanoma that has been completely resected, rendering them free of disease.

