STUDY DRUGS, DOSES AND MODE OF ADMINISTRATION

NIVOLUMAB will be supplied as a sterile, preservative-free solution in 10 mL vials at a concentration of 10 mg/mL; which, in cycle 1, based on the subject's weight, may be diluted with sterile normal saline (0.9% sodium chloride). NIVOLUMAB (3 mg/kg) will be administered as a 30-minute i.v. infusion.

Starting 4 weeks after the last co-administered dose in cycle 1, subjects will be administered a flat dose 480 mg nivolumab IV every 4 weeks (Q4W) in cycles 2-5.

Ipilimumab will be supplied as a sterile, preservative-free solution in 10mL (50 mg) or 40 mL (200 mg) vials at a concentration of 5 mg/mL; which, based on the subject's weight, may be diluted with sterile normal saline (0.9% sodium chloride). Ipilimumab (1 mg/kg) will be administered as a 30-minute i.v. infusion.

On days when both study drugs are administered, nivolumab (BMS-936558) will be given before the ipilimumab.

DURATION OF TREATMENT/STUDY PARTICIPATION

The expected maximum duration of nivolumab treatment for a subject is 60 weeks. The expected maximum duration of ipilimumab treatment for a subject is 12 weeks.

The expected maximum duration of a subject's participation in this study is 3 years.

CRITERIA FOR EVALUATION

Safety

Evaluation of safety and tolerability will include ongoing review of clinical laboratory tests (blood and urine sampling for clinical laboratory parameters), pregnancy testing, Eastern Cooperative Oncology Group (ECOG) performance status, physical examination including vital sign measurements, electrocardiogram (ECG), chest radiography, and adverse events. Safety will also include evaluations of immune safety and immunogenicity.

Dose-limiting Toxicity

A DLT is defined as a NIVOLUMAB and/or ipilimumab-related \geq Grade 3 adverse event occurring within 29 days after the first dose of study drugs excluding: Grade 3 adverse event of tumor flare (defined

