i.v.	intravenous, intravenously
ICF	informed consent form
ICH	International Conference on Harmonisation
IL-2	interleukin-2
INF	Interferon
irAE	Immune-related adverse event
IRB	Institutional Review Board
irCR	Immune-related complete response
irPD	Immune-related progressive disease
irPR	Immune-related partial response

Abbreviation	Term
irRC	Immune-related Response Criteria
irSD	Immune-related stable disease
mAb	monoclonal antibody
NIVOLUMAB	PD-1-specific, fully human IgG4 mAb
MedDRA	Medical Dictionary for Regulatory Activities
mWHO	Modified World Health Organization
MPR	Mixed Lymphocyte Reaction
MTD	maximum tolerated dose
NCI	National Cancer Institute
PBMC	peripheral blood mononuclear cells
PCC	Perlmutter Cancer Center
PD-1	Programmed Death-1
PD-L1	Programmed Death-Ligand 1
PI	Propidium Iodide
PR	Partial Response
PVG	Pharmacovigilance
SAE	serious adverse event
RECIST	Response Evaluation Criteria in Solid Tumors
SOC	system/organ/class
SOP	standard operating procedure
SPD	Sum of Product Diameters
SSAE	Serious or Significant Adverse Event
TEAE	treatment-emergent adverse event
TNF	tumor necrosis factor
ULN	upper limit of normal
URTI	upper respiratory tract infection
US	United States of America
UTI	urinary tract infection
WBC	white blood cell
WHO	World Health Organization

TABLE 1: TIME AND EVENTS SCHEDULE

Examination	Screening	Cycle 1 Treatment Period ^{11, 13} (Visits must occur ± 7 days of the scheduled visit)					Cycle 2-5 Treatment Period ^{11, 13} (Visits must occur ± 7 days of scheduled visit; Every 4 weeks for 48 weeks)						Study Completion/ Early Withdrawal (Visit to occur 12 week ± week after last dose)	Survival Follow-up	
		2	3	4	5	6	7	8	9	10	11	12			
Visit	1	2	3	4	5	6	7	8	9	10	11	12			
Week	-1	1	4	7	10	12									
Timepoint (Day)	-28 to -1	1	22	43	64	78									
Research Procedures															
• Sample for immunogenicity ⁷		•			•							•	• 1 3	•	
• Serum for cytokine panel ⁷		•			•							•	• 1 3	•	
• Cellular immune assays ⁷		•			•							•	• 1 3	•	
• Cryopreserved serum ⁷		•			•							•	• 1 3	•	
• Tissue Submission ¹ 4		•	• ¹⁵	• ¹⁵	• ¹⁵	• ¹⁵	• ¹⁵	• ¹⁵	• 1 5		• ¹⁵				

Efficacy Procedures																	
CT/MRI (neck, chest, abdomen, pelvis) ^{9, 12}	•					•	•						•	•			
							1							1			
							4							4			
															•		•
CT/MRI (Brain)	•					•	•						•	•			
							1							1			
							4							4			•
Follow-up contact ¹⁰																	•
Study Drug Administration																	
Ipilimumab ¹¹		•	•	•	•												

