- ¹⁰ Survival statuses for all patients who have discontinued from study treatment will be collected every 6 months (+/- 1 month) until death, lost to follow-up, or withdrawal of consent for survival follow-up. Follow-up contact may be done in person at the study center or by telephone; survival information may be obtained from family members or other medical professionals caring for the patient. Survival information including post-study treatment modalities and date and site of disease progression will be documented in the source documents and survival eCRF. Social security death index (SSDI) and other public records will be used if necessary to confirm survival status and/or date of death.
- ¹¹ There is only one 12 week induction treatment cycle (cycle 1). The ipilimumab will be at 1 mg/kg every 3 weeks for 4 doses during the 12 week induction cycle, and NIVOLUMAB will be at 3 mg/kg every 3 weeks for 4 doses during the 12 week induction treatment cycle then at 480mg every 4 weeks for 48 weeks during cycles 2-5.
- ¹² To be obtained every 12 weeks. Patients that discontinue therapy for any reason will only have the immunology procedures collected at the next mandated protocol timepoint, but not thereafter.
- ¹³ Radiology exams will be completed prior to dosing at week 12 and every 12 weeks prior to each dosing visit.
- ¹⁴ Tissue will be submitted, if available, as outlined in section 5.6.1
- ¹⁵ Tissue from any post-relapse biopsy will be requested for analysis by immunohistochemistry as outlined in section 5.6.1.

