4.2.4.1. Definition

A DLT is defined as a NIVOLUMAB or NIVOLUMAB with ipilimumab related Grade 3 or greater adverse event other than the exceptions noted occurring within 29 days after the first dose excluding: Grade 3 adverse event of tumor flare (defined as local pain, irritation, or rash localized at sites of known or suspected tumor), Grade 3 rash, Grade 3 immune-related adverse event (irAE, defined below) that resolves to a Grade 1 or less within 28 days, or a transient (resolving within 6 hours of onset) Grade 3 infusion-related adverse event. A Grade 3 irAE that resolves to a Grade 1 or less within 28 days, while not constituting a DLT for dose escalation purposes, may preclude further administration of NIVOLUMAB and/or ipilimumab to the subject.

The following are excluded from the definition of a DLT:

- Grade 3 rash,
- Grade 3 irAE that resolves to a Grade 1 or less within 28 days, or
- A transient (resolving within 6 hours of onset) Grade 3 infusion-related adverse event.

A Grade 3 irAE that resolves to a Grade 1 or less within 28 days, while not constituting a DLT, may preclude further administration of the study drugs to the subject. A DLT will be considered related to 1 or both study drugs unless there is a clear, well-documented, alternative explanation for the toxicity.

Toxicities occurring more than 28 days after the first dose will be monitored and discussed with BMS.

All adverse events that meet DLT criteria, as well as any Grade 3 or 4 infusion reactions whether or not the event is a DLT, must be reported using the rapid notification procedures described in Section 9.6.

Patients who discontinue treatment for toxicities will continue on the protocol radiology evaluation schedule every 12 weeks once the toxicity resolves to obtain relapse-free survival data.

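### Section 4.2.5 counts DLTs over the 12 weeks of Cycle 1, but the DLT definition ends 29 days after the first dose; taken literally, the only rate-based accrual limit cannot count toxicity after combination doses 3 and 4.

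*Combined protocol and SAP*

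**What the plan says.** The accrual rule in Section 4.2.5 sets two early limits, at three patients with a DLT among the initial six and at four among the initial ten. The limit for the full cohort reads: "40% of subjects or more in this cohort of 20 patients experiences a DLT during Cycle 1, accrual will stop". The stop lasts until the sponsor, BMS and the FDA have consulted.

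The DLT definition in Section 4.2.4.1 covers a related Grade 3 or higher "adverse event other than the exceptions noted occurring within 29 days after the first dose". The synopsis has the same limit: "Grade 3 adverse event occurring within 29 days after the first dose of study drugs". Both exclude Grade 3 rash, a Grade 3 irAE that settles to Grade 1 or less within 28 days, and a transient Grade 3 infusion event. Both then add: "Toxicities occurring more than 28 days after the first dose will be monitored and discussed with BMS".

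The synopsis design overview and Section 2.1 use the term differently: "Patients who experience a DLT to NIVOLUMAB and ipilimumab during or after cycle 1 will not receive further treatment". Section 4.2.4.1 also keeps the phrase "while not constituting a DLT for dose escalation purposes", although Section 4.3 gives every patient the same regimen.

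Table 1 places the four combination doses on Days 1, 22, 43 and 64 and the Week 12 visit on Day 78. Its footnote 11 confirms a single 12-week induction cycle, and its header says "Visits must occur ± 7 days of the scheduled visit".

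**The concern.** Safety and tolerability is the primary objective (Section 1.5), and Section 4.2.5 is the only place where a toxicity rate limits accrual. The rule names a 12-week period, while the event it counts is defined over about a third of that period. Two people applying the text in good faith to the same data could reach different counts.

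The later part of Cycle 1 matters on the protocol's own account. Section 2.4.2 says that irAEs with ipilimumab tend to appear after repeated dosing, although the same sentence calls them mostly low grade and self-limited. Section 1.4.3 chose the present doses on 12-week tolerability. In cohort 4 of the predecessor trial, at the reversed doses, toxicity kept 10 of 20 patients from finishing 12 weeks. In cohort 5, at the present doses, 17 of 20 continued past 12 weeks.

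The definition also affects replacement. Section 4.9 replaces a patient withdrawn from the study before the end of the first cycle for any reason other than a DLT. If the 29-day definition governs, a patient withdrawn in Week 8 for severe toxicity has no DLT and is replaced. That patient stays in the Safety Population but drops out of the count for Section 4.2.5.

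**Working it through.** **Timing.** Inputs are the 29-day window (Section 4.2.4.1), the dose days and the visit window of 7 days either way (Table 1).

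- End of DLT window: Day 1 + 29 = Day 30.
- Dose 2, nominal Day 22: 30 − 22 = 8 days of observation inside the window.
- Dose 3, earliest: 43 − 7 = Day 36, outside.
- Dose 4, earliest: 64 − 7 = Day 57, outside.
- Share of Cycle 1 covered: 29/84 = 35%.

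This part needs no assumption. The later sentence about 28 days is not a second definition. It describes how later toxicity is handled and differs from the definition by one day.

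**Effect on the rule.** The plan gives no stopping probability or error rate, so there is no figure to reproduce. Read 40% of 20 as 0.40 × 20 = 8. Let *r* be the true 12-week rate of events meeting the DLT grade and exclusion criteria, and *s* the share with onset inside 29 days. The rate the rule sees is *c* = *r* × *s*. For independent patients, the chance of ever meeting a limit is an exact binomial recursion that stops at 3 within the first 6, 4 within 10 or 8 within 20. Replacements are not modelled.

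First limit at *c* = 0.15:

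1 − [0.85⁶ + 6(0.15)(0.85⁵) + 15(0.15²)(0.85⁴)] = 1 − [0.3771 + 0.3993 + 0.1762] = 0.047.

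Adding the second and third limits raises this to 0.072 and 0.073.

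The documents do not give *s*. It is assumed here over a range; 35% is the value if onset were uniform over 84 days.

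| True 12-week rate *r* | *s* = 100% | 75% | 50% | 35% | 25% |
|---|---|---|---|---|---|
| 15% | 7.3% | 3.2% | 0.95% | 0.3% | 0.1% |
| 30% | 44% | 22% | 7.3% | 2.5% | 0.95% |
| 50% | 93% | 67% | 29% | 11% | 4.3% |

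The 15% row is (20 − 17)/20 from cohort 5, where the reasons for not continuing are not stated. The 50% row is 10/20 from cohort 4, used only as an unacceptable case. Neither is a DLT rate.

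The recursion reaches a 50% chance at *c* = 31.9%. Dividing by the share gives the true rate needed for an even chance of a pause: 31.9% at *s* = 100%, 42% at 75% (0.319/0.75) and 64% at 50% (0.319/0.50). At 25% no true rate reaches it (0.319/0.25 exceeds 1).

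**The case against.** The strongest reply is that there is one DLT definition, stated consistently as 29 days, and that the rest is loose wording. That is largely right. A reader might infer that the protocol has several competing DLT windows, but the documents do not support this. The 28-day line concerns handling of later events, and the phrase about a DLT during or after Cycle 1 governs treatment of the individual patient. What stands is that Section 4.2.5 itself names a period the definition does not cover, and that a DLT after Cycle 1 cannot exist under that definition.

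Second, if Section 4.2.5 is read as applying the DLT criteria throughout Cycle 1, nothing is lost. That is also right. The text does not settle which reading governs, and that is the defect.

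Third, the size is hypothetical. The share is assumed, and non-completion may overstate the DLT rate, because excluded Grade 3 irAEs can still end a patient's treatment. At a 12-week DLT rate of 10% or 5% the rule fires 2.3% or 0.3% of the time even with every event counted. The table also treats outcomes as known at once, so it gives the chance that a limit is ever met and not the chance that accrual is cut early. All of this stands.

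Fourth, a reader might infer that toxicity after Day 29 is unmonitored. It is not. The investigator reviews adverse events monthly (Section 6.12) and the DSMC evaluates all SAEs (Section 6.8). The DSMC also reviews safety data, at an interval given both as every 6–8 weeks (Section 6.12.1) and as twice a year (Sections 6.12, 6.12.1 and 8.1). Section 6.11 requires rapid notification, Section 4.2.1.3 stops individual patients, and Section 4.2.5.1 holds enrollment for two specific Grade 4–5 events. None of these sets a rate limit.

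Fifth, a 12-week window has its own short tail. From dose 4 on Day 64 to the visit on Day 78 is 14 days, or 7 if the dose is a week late. Section 4.2.1.2 also lets delays move the schedule, so Week 12 is not a fixed end. This stands and shapes the fix.

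**Conclusion.** The contradiction is in the text and rests on no assumption: the rule counts over Cycle 1, and the event it counts ends about Day 30, before dose 3 can be given. It should be corrected, because it concerns the only rate-based accrual limit in a trial whose primary objective is safety.

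The practical loss is uncertain. It is nil if the Cycle 1 wording governs or if all qualifying events occur early. In absolute terms it is small if the regimen is as tolerable as cohort 5 suggests: 7.3% against 0.1% to 3.2% at a 15% rate and shares of 25% to 75%. It is large only if the regimen is clearly worse: 93% against 4% to 67% at a 50% rate. A reader might take these figures as estimates of how often the rule will fail. The documents do not support that, since they give neither the timing of onset nor a DLT rate for this regimen.

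**What to change.** 1. In Section 4.2.5, count events that meet the DLT grade and exclusion criteria with onset from the first dose to the end of Cycle 1. Define that end as the Week 12 assessment or, if doses are delayed, a stated interval after the last combination dose. The sponsor must choose the interval, since the documents give none.
2. Align Section 4.2.4.1, Section 2.1 and the synopsis to this. Remove the 28/29-day mismatch and the leftover dose-escalation phrase. State that a later event meeting the same criteria still stops that patient's treatment but does not count toward Section 4.2.5.
3. Keep the limits, written as 3 of the first 6, 4 of the first 10 and 8 of 20 treated patients. Count any patient with a qualifying event and do not replace that patient under Section 4.9.

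Stating instead that Section 4.2.5 counts 29-day DLTs only would also end the contradiction, but it would leave the limit blind to doses 3 and 4.

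The cost is amendment wording, with no extra patients, visits or tests. There are two downsides. Each patient takes 12 weeks to evaluate instead of about 4, plus up to 28 days to classify a late Grade 3 irAE, so up to about 16 weeks. Section 4.2.5 has no enrollment hold meanwhile, so a limit may be met after more patients have entered. The chance of a pause also rises compared with the 29-day reading, to 7.3% at the illustrative 15% rate. That pause is for consultation and does not end the trial.

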4.2.5.1. Other Stopping Rules During Enrollment

Enrollment will be held at any time during the study if either of the following study drug-related, Grade 4 or 5 toxicities occurs:

- colitis with perforation and/or requiring colectomy, or
- hepatic failure.

The Sponsor-investigator will discuss such cases with BMS to decide whether to resume enrollment and/or to jointly discuss such cases with the FDA. IRBs will be notified by the Sponsor-investigator of all cases and decisions regarding continued enrollment.

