6.10. Immune-related Adverse Events

An irAE, a subset of adverse events, is defined as a clinically significant adverse event of any organ that is associated with study drug exposure, of unknown etiology, and is consistent with an immune-mediated mechanism. Appropriate efforts should be made to rule out neoplastic, infectious, metabolic, toxin, or other etiologic causes of the irAE.

Given the intended mechanism of action of NIVOLUMAB and/or ipilimumab, namely disinhibition of cellular immune responses, it is possible that syndromes may develop that are most consistent with an underlying enhanced immune response as the driving factor. Such events may consist of persistent rash, diarrhea and colitis, autoimmune hepatitis, arthritis, glomerulonephritis, or cardiomyopathy. The spectrum of irAEs is currently hypothetical, as very few human subjects have been treated to date, and are based upon preclinical studies in mice deficient in PD-1, as well as experience with other monoclonal antibodies that act by disinhibiting the immune response. Such irAEs may resolve with time, or may require institution of counteracting immunosuppressive therapies.

BMS has observed irAEs in another development program with the immunostimulatory antibody, ipilimumab (anti-CTLA-4). Ipilimumab-induced irAEs are typically low grade and self limited, more often occur after multiple doses, and most frequently involve the gastrointestinal tract (diarrhea/colitis), skin (rashes), liver (hepatitis), and endocrine systems (a variety of endocrinopathies). In addition, the known animal and human toxicity profiles of anti-CTLA-4 antibodies such as ipilimumab include colitis as an expected adverse event. Based on these considerations, NIVOLUMAB may also cause immune-mediated colitis. Uveitis and visual changes may also be seen.

Colitis is characterized by new onset of diarrhea, which may be accompanied by abdominal pain and or gastrointestinal bleeding. Events of Grade 3 or Grade 4 diarrhea as well as Grade 2 diarrhea with blood in stool should be evaluated for colitis. All adverse events of colitis \geq Grade 2 are deemed to be of special interest, and should be reported to BMS within 24 hours of occurrence using the serious adverse event reporting procedures (Described in Section 8.3), even if the adverse event itself is not deemed as serious.

Management Algorithms for High Grade irAEs

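### A study-drug-related death triggers no automatic hold on enrollment unless its cause is one of two named toxicities, and no DSMC recommendation is required before accrual resumes

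*Combined protocol and SAP*

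**What the plan says.** Two sections can stop accrual.

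- **Section 4.2.5.1** sets an immediate hold: "Enrollment will be held at any time during the study if either of the following study drug-related, Grade 4 or 5 toxicities occurs". The first entry in the list is "colitis with perforation and/or requiring colectomy, or" and the second, which is the last, is "hepatic failure". On restarting: "The Sponsor-investigator will discuss such cases with BMS to decide whether to resume enrollment", with joint discussion with the FDA as a further option. IRBs are told of all cases and decisions.
- **Section 4.2.5** sets the count rule: "If 3 or more of the first 6 subjects or 4 or more of the first 10 or 40% of subjects or more". The same sentence then fixes the denominator of the last limit, the window and the consequence: "in this cohort of 20 patients experiences a DLT during Cycle 1, accrual will stop". The sponsor, BMS and the FDA must confer before it restarts.

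Section 4.2.4.1 defines a DLT as a related event of Grade 3 or higher, with listed exceptions, within 29 days of the first dose. Toxicities later than 28 days are to be followed and taken up with BMS; no hold is attached to them. Section 2.5 gives a maximum of 60 weeks of nivolumab.

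Section 6.8 requires fatal and life-threatening events to be reported immediately, the DSMC and IRB to be informed, and all SAEs to be evaluated by the DSMC. Section 6.12.1 allows extra DSMC reviews. Section 6.8.3 mentions a sponsor-investigator decision to halt a study, and Section 12.2 preserves the freedom to act at once for safety.

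**The concern.** The hold is defined by cause rather than by outcome. Followed literally, a non-fatal colectomy for drug-related Grade 4 colitis stops enrollment automatically, while a fatal drug-related event in another organ does not. The protocol itself expects that other organs may be affected: Section 6.10 lists "persistent rash, diarrhea and colitis, autoimmune hepatitis, arthritis, glomerulonephritis, or cardiomyopathy", Section 2.4.2 adds irregular heart rhythm and heart attack, and Section 4.2.1.2 refers to management algorithms for pulmonary, neurological and renal toxicity.

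Safety and tolerability is the primary objective (Section 1.5). The patients are free of disease after resection and may be as young as 16 (Section 3.1). A related death in such a population is the event after which one would most expect enrollment to wait for a review. The plan leaves that to discretion.

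The second part concerns restarting. After a hold under 4.2.5.1, the stated decision-makers are the sponsor-investigator, who is also the investigator making the treatment decisions (Synopsis, Efficacy), and BMS, which supplies the drugs and funds the trial (Sections 4.1 and 10.1). Section 6.12.1 makes the DSMC responsible for monitoring safety, yet neither stopping section states that its recommendation is needed.

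**Working it through.** The plan gives no operating characteristics for either rule and no expected death rate, so there is no stated figure to reproduce.

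**Step 1. How a related death from an unlisted cause is counted.**

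| Timing of death | 4.2.5.1 hold | DLTs counted (4.2.4.1) |
|---|---|---|
| Within 29 days of first dose | No | 1, the same weight as a qualifying Grade 3 event |
| Later, while treatment runs to 60 weeks | No | 0 |

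**Step 2. Limits of the count rule (4.2.5).** These are 3 of the first 6, 4 of the first 10, and 40% of the cohort of 20, which is 0.40 × 20 = 8.

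**Step 3. Two such deaths in the first 6, no third DLT among them.** 2 < 3; 2 < 4; 2 < 8; and 2/6 = 33.3% < 40%. No limit is met and accrual stays open. If both deaths fall after the 29-day window, the DLT count is 0.

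**Step 4. Largest number that passes.** At most 2 in the first 6, 3 in the first 10 and 7 in 20. Seven in 20 (35%) passes only if no more than 2 fall in the first 6, no more than 3 in the first 10, and there is no other DLT.

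**Step 5. Two points of reading.**

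- The 40% limit is taken as 8 of the cohort of 20, which is how the sentence reads. As a running share it would stop accrual at 2 of 5 (40%), or even at 1 of 2 (50%), and would make the 3-of-6 (50%) and 4-of-10 (40%) limits redundant.
- Section 4.2.5 counts DLTs during Cycle 1, which is 12 weeks, whereas 4.2.4.1 defines them within 29 days. Two deaths are below 3 on either window.

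**Step 6. Illustration under assumed rates.** Let *q* be the probability that a patient dies of an unlisted drug-related cause. The documents do not give *q*; the values below are assumptions. All such deaths are taken to count as DLTs, and no other DLT occurs.

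- At least one death in 20: 1 − (1 − *q*)^20. For *q* = 0.02, 1 − 0.98^20 = 0.332.
- Exactly 2 of the first 6: 15 × *q*² × (1 − *q*)⁴. For *q* = 0.05, 15 × 0.0025 × 0.8145 = 0.031.
- Count rule stops accrual by patient 20: exact recursion, checking the three limits after each patient.

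| Assumed *q* | At least 1 death in 20 | Exactly 2 of first 6 | Count rule stops on these deaths alone |
|---|---|---|---|
| 1% | 18.2% | 0.14% | under 0.01% |
| 2% | 33.2% | 0.55% | 0.02% |
| 5% | 64.2% | 3.1% | 0.28% |
| 10% | 87.8% | 9.8% | 2.2% |

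The first column is the chance that a death trigger would come into play, provided each death occurs while enrollment is open. The last shows that the count rule is no substitute for one.

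**The case against.** The best defence is that the missing element is only automaticity within a working safety system. A fatal event is reported immediately, the DSMC and IRB are informed, and the DSMC evaluates every SAE (Section 6.8). Suspected, unexpected fatal events go to the FDA within 7 days (Section 6.8.2). Extra DSMC reviews can be called (6.12.1), and the sponsor-investigator or BMS can act at once (6.8.3, 12.2). Both drugs are approved, and Section 1.4.3 reports 20 patients already treated at these induction doses. Two deaths in six patients is improbable at low death rates, and a third DLT among the six would stop accrual.

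Most of this stands and limits the point. It does not close the gap, because every one of these provisions permits a pause and none requires one. Scheduled DSMC review cannot be relied on to come first: Sections 6.12 and 8.1 say twice a year, while 6.12.1 gives both that and every 6 to 8 weeks.

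Three stronger readings are tempting, and the documents do not support them.

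- **That the trial would carry on regardless after such a death.** The text permits a pause and fixes no order between review and the next enrollment.
- **That a restart involves no outside body, or that the DSMC has no role.** FDA consultation is mandatory under 4.2.5 and optional under 4.2.5.1, IRBs are notified under 4.2.5.1, and the DSMC evaluates all SAEs. What is absent is a stated DSMC recommendation on resuming.
- **That cytokine storm is one of the risks left uncovered.** Section 2.4.2 says it is not expected with these drugs.

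**Conclusion.** The point holds as a statement about the prespecified rules. A drug-related death from a cause other than the two listed triggers no automatic hold. It adds one DLT within 29 days of the first dose and none afterwards. On those deaths alone the count rule tolerates 2 in 6, 3 in 10 or 7 in 20, subject to the conditions in Steps 3 and 4. These counts are boundary cases, not forecasts. They rest on reading the 40% limit as 8 of 20 and on there being no further DLTs. The percentages in Step 6 rest wholly on assumed death rates.

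This is a weakness of trial governance rather than an error in an analysis or a stated figure. It is worth correcting because the remedy is specific and cheap, and because safety is the primary objective in patients who are free of disease.

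**What to change.** 1. In Section 4.2.5.1, add a third trigger for holding enrollment: any death judged related to study drug (Grade 5, any cause, at any time while enrollment is open), with enrollment held until the case has been reviewed.
2. In Sections 4.2.5 and 4.2.5.1, state that accrual resumes only after a documented recommendation from the existing DSMC, in addition to the BMS, FDA and IRB steps already listed.
3. Separately, reconcile the 29-day DLT window in Section 4.2.4.1 with the Cycle 1 window in Section 4.2.5, so that it is clear which events enter the count.

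Items 1 and 2 concern enrollment and its oversight; they change no dose and no individual patient's treatment. The cost is an amendment and, if such a death occurs, an unscheduled meeting of a committee already in place. The downside is a possible short pause in accrual.
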